11.7 Follow-up Investigation of Adverse Events

The investigators must follow up AEs until recovery as a general result or disease condition is stabilized, except for the following cases, and must report the additional information on the disease condition resulted from the follow-up investigation to the sponsor.

- The principal investigator or subinvestigators judges that the outcome of the AE cannot be recorded because the AE is permanent with no prospect of recovery, etc.
- The AE is exacerbation of pre-existing complication.
- The subject is lost to follow-up.

- 99 -

- The principal investigator or subinvestigators judges that a follow-up investigation until recovery is unnecessary.

AEs sustained at the end of the clinical trial or discontinuation of the trial, except for the above-mentioned cases, should be followed up until recovery or the disease condition is stabilized.

The study sites must submit source documents required for event adjudication by CEC of all death cases and cases with stroke occurred up to 1 year post-procedure via the monitor as much as possible. The source documents required for event adjudication are as shown in Table 13-1, but not limited to those. When provision of additional information is requested by the CEC, the study sites should respond as much as possible.

Table 13-1: Source documents required for event adjudication by CEC

Time of death	Time of stroke onset

 Death certificate Autopsy record¹ Discharge record 	
 Head neuroimaging (head CT/MRI)² Medical record Medical record by a neurologist/neurosurgeon mRS

¹When available

13.2 Echo Core Laboratory

To avoid bias among study sites and physicians, and to ensure consistent and objective evaluation, the echocardiographic parameters including EOA will be measured and evaluated by an echocardiography core laboratory that is independent from the study organization including the sponsor and study sites. The echocardiography core laboratory will appropriately measure/evaluate the echocardiographic parameters including EOA of all enrolled subjects in this clinical trial (including the continued access registry), using the echocardiographic imaging data at baseline, 30 days post-procedure, 6 months post-procedure, and 1 to 5 years post-procedure annually. For details, see the "Echo Core Laboratory Procedure."

The study sites should provide the echocardiographic imaging data (CD-ROM or DVD) at baseline, 30 days post-procedure, 6 months post-procedure, and 1 to 5 years post-procedure annually to the Echo Core Laboratory via the monitor.

12 MONITORING OF THE CLINICAL TRIAL BY DATA MONITORING COMMITTEE

To ensure the safety of the subjects and ensure the ethical and scientific validity of the conduct of this clinical trial, Data Monitoring Committee (DMC) independent from the study organization including the sponsor and study sites will evaluate the intermediate data during the trial. The DMC consists of at least 3 members, including physicians with expertise in the present disease area and study treatment and a clinical statistician, monitors as to whether the clinical trial is conducted safely and appropriately, and give advice and recommendations to the sponsor for changes to the protocol and as to whether the trial should be continued or not. The monitoring of this clinical trial by the DMC will be continued until the end of the enrollment in the continued access registry, and may be extended as needed. For DMC opening requirements and detailed activities and operating procedure, see "EWJ-003 Data Monitoring Committee Procedure."

When provision of information including autopsy records, etc. is requested by the DMC, the study sites should respond as much as possible.

13 EVALUATION BY THIRD-PARTY JUDGMENT ORGANIZATION

13.1 Clinical Event Adjudication Committee

To avoid bias among study sites and physicians, and to ensure consistent and objective evaluation, the major clinical events reported by the study sites will be assessed by Clinical Event Committee (CEC) that is independent from the study organization including the sponsor and study sites. The CEC consists of at least 1 member with expertise in this present disease area and study treatment, and at least 1 member with expertise in neurological disease area, and as shown below, performs review and adjudication of all death cases and cases with stroke occurred in all enrolled subjects in this clinical trial (including continued access registry) up to 1 year post-procedure. For CEC opening requirements and detailed activities and operating procedure, see "EWJ-003 Clinical Event Adjudication Procedure."

- Death

For all death cases reported by the study sites within 1 year post-procedure, the CEC will adjudicates the cause of death (cardiovascular or non-cardiovascular death) and the causal relationship to the study device and study procedure, in accordance with VARC-2 guideline⁵⁶¹ (see Section 30 "GLOSSARY").

- Stroke

For all stroke cases reported by the study sites within 1 year post-procedure, the CEC will adjudicates the events (disabling stroke or non-disabling stroke) and the causal relationship to the study device and study procedure, in accordance with VARC-2 guideline⁵⁶¹ (see Section 30 "GLOSSARY").

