Stroke/transient ischemic attack	
<Stroke/transient ischemic attack diagnostic criteria>
 
Acute onset of a local or general neurological disorder, with at least one of the followings: changes in the conscious level, hemiplegia, hemiparesis, numbness, sensory loss affecting one side of the body, dysphasia or aphasia, hemianopia, amaurosis fugax, and other neurological signs or symptoms consistent with stroke.
 
Stroke: Local or general neurological disorder sustains ≥ 24 hours, or even < 24 hours new hemorrhage or infarction is found by head neuroimaging, or a neurological disorder resulted in death.
 
Transient ischemic attack: Local or general neurological disorder sustains < 24 hours, with no new hemorrhage or infarction by head neuroimaging.
 
As for clinical findings, the absence of causes other than stroke that can be easily identified (brain tumor, trauma, infection, hypoglycemia, peripheral lesion, influence of drug, etc.) must have been determined by a neurologist or together with a neurologist*. Definitive diagnosis should be made by at least one of the followings:
 
 • Diagnosis by a neurologist or neurosurgeon • Head neuroimaging (CT scan or brain MRI); however stroke may be diagnosed only by the clinical findings 
* Do not report non-local encephalopathy as stroke, unless findings of cerebral infarction are present based on the head neuroimaging (CT scan or brain MRI).
 
<Stroke classification>
 
Ischemic: Acute angiopathy at the local brain, spinal cord, or retina associated with infarction in the central nervous system tissues
 
Hemorrhagic: Acute angiopathy at the local or general brain or spinal cord associated with hemorrhage in the cerebral parenchyma, cerebral ventricle, or
	VARC-2												

Term	Definition	Reference/rationale
	
subarachnoid
 
If the information is inadequate for determining ischemic or hemorrhagic, classify as cause unknown.
 
<Definition of stroke> Stroke is classified into disabling or non-disabling.
 
 • Disabling stroke At 90 days after the onset of a stroke, $mRS \geq 2$, and exacerbation ≥ 1 in the mRS from before the onset. • Non-disabling stroke At 90 days after the onset of a stroke, $mRS < 2$, and no exacerbation ≥ 1 in the mRS from before the onset. 	

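### The event committee is sent only deaths and events the site already calls stroke, so a non-fatal stroke that a site under-recognises has no stated route into the stroke results

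*Combined protocol and SAP*

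**What the plan says.** Section 13.1 sets up a committee independent of sponsor and sites, so that major events are judged consistently and without bias between sites. Its general remit is already tied to site reporting: "major clinical events reported by the study sites will be assessed by Clinical Event Committee (CEC"). Within that remit it "performs review and adjudication of all death cases and cases with stroke occurred in all enrolled subjects in this clinical trial", registry included, up to 1 year.

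For stroke, the trigger and the first ruling are: "For all stroke cases reported by the study sites within 1 year post-procedure, the CEC will adjudicates the events (disabling stroke or non-disabling stroke"). The sentence continues "and the causal relationship to the study device and study procedure, in accordance with VARC-2 guideline", with a pointer to the Glossary. For deaths, the ruling is cardiovascular or non-cardiovascular, plus causality.

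The paragraph introducing Table 13-1 sets the matching paperwork rule. Sites "must submit source documents required for event adjudication by CEC of all death cases and cases with stroke occurred up to 1 year post-procedure". It adds: "When provision of additional information is requested by the CEC, the study sites should respond as much as possible".

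The Glossary (Section 30) separates stroke from TIA by duration and imaging. A deficit of 24 hours or more is a stroke; "or even < 24 hours new hemorrhage or infarction is found by head neuroimaging", it is also a stroke; a neurological disorder ending in death is a stroke as well. TIA is a shorter deficit with no new lesion. Sites are told not to report non-local encephalopathy as stroke unless imaging shows infarction.

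Stroke and the death-and-stroke composite are secondary safety endpoints (Section 9.2.1). TIA is not a listed endpoint. Section 15.1.2 says secondary endpoints are described, not tested.

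**The concern.** The events most open to disagreement between sites are those near the stroke boundary: a short deficit with a small new lesion, or a confusional state with infarction on imaging. In an open, single-arm trial, the written rule leaves that first decision with the site and brings in the independent committee only once the answer is stroke. The committee can then grade the event and rule on causality. It is given no stated way to find a stroke filed as something else.

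At stake are the 1-year stroke rate and the death-and-stroke composite. Both go into the 1-year report that supports the approval application (Section 18.3). Because TIA is not an endpoint, a stroke filed as TIA leaves the endpoint tables and remains only as an adverse event.

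The next subsection of the protocol takes the broader approach. In Section 13.2 the echo core laboratory receives images from all enrolled subjects at fixed visits, whatever the site's own reading.

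**Working it through.** **1. Trace each kind of event up to 1 year through the written rules.**

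| Event | Glossary class | Stated route to the CEC | Stated ruling |
|---|---|---|---|
| Non-fatal, site reports stroke | Stroke | Yes | Disabling or not; causality |
| Fatal neurological disorder, any site label | Stroke | Yes, as a death | Cardiovascular or not; causality |
| Non-fatal, under 24 hours, new lesion, site reports TIA | Stroke | None | None |
| Non-fatal, non-local encephalopathy with infarction on imaging, site reports encephalopathy | Reporting as stroke not barred | None | None |

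The last two rows are the gap. In the composite, such a case is lost only if the subject is still alive at the time point, since a death would be counted anyway.

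**2. Check whether scheduled tests close the gap.** In the main cohort, NIHSS, mRS and head CT are done at 30 days, 6 months and 1 year (Sections 10.2.5 to 10.2.7). They help a site recognise a stroke, but no finding is said to trigger referral. In the continued access registry all subjects have them at 30 days (Section 10.3.5). At 6 months and 1 year only subjects already diagnosed with stroke do (Sections 10.3.6 and 10.3.7).

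**3. The plan's own figures.** There is no design figure for stroke. The only one is the power of the mortality test. With 24 subjects, a performance goal of 45%, expected mortality of 20% and one-sided 0.05, the exact binomial test rejects at 6 or fewer deaths, with type I error 0.0364 and power 0.8111. This matches the stated 81.1%. Nothing here depends on stroke labels.

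**4. Size of one event.**
- Main cohort, N = 30: 1/30 = 3.3% (exact 95% CI 0.1% to 17.2%); 2/30 = 6.7% (0.8% to 22.1%). The difference is 3.3 points.
- Registry, at its maximum of 50: 1/50 = 2.0 points.

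**5. Expected number of strokes.** Section 1.2.2.1 gives overall 1-year stroke rates of 4.3% (US trial of this device) and 5.4% (European and Canadian trial). 30 × 0.043 = 1.29; 30 × 0.054 = 1.62.

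**6. Chance of at least one stroke filed under another label.** Let p be the true 1-year stroke rate and m the share that sites label otherwise. Then P = 1 − (1 − p·m)^30. The documents give no value for m; 10% to 50% is an assumption.

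| p | m = 10% | m = 25% | m = 50% |
|---|---|---|---|
| 4.3% | 12.1% | 27.7% | 47.9% |
| 5.4% | 15.0% | 33.5% | 56.0% |

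**The case against.** The strongest reply is that the boundary is not left to site habit. The Glossary gives every site the same rule and requires a neurologist to make, or share in, the exclusion of other causes. A site that filed a short deficit with a new lesion as TIA would be misapplying the protocol. Scheduled examinations are done by a neurologist, neurosurgeon or suitably able physician. All adverse events are recorded (Section 11.6), monitors check source documents (Section 22.1.1), and an independent monitoring committee looks at interim data (Section 12). All this stands, and it lowers the chance of an error. None of it sends a disputed event to the CEC.

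Second, operating detail is in a separate CEC procedure that is not among the documents, and it may add triggers. That also stands. But Section 13.1 and the Table 13-1 text define what is reviewed and what sites must send. The power to ask for more information is not said to extend to events never sent.

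Third, the endpoint is descriptive, no decision rule uses it, and the two intervals in step 4 overlap almost entirely. This limits the importance of the point but does not remove the gap.

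A reader might infer three stronger things that the text does not support:
- That the CEC rules only on disabling status. The same sentence adds causality under VARC-2 and points to the Glossary.
- That a mislabelled stroke can never reach the CEC. A fatal case arrives as a death, and the unseen procedure may provide other routes.
- That the stroke count can only be corrected downward. No not-a-stroke outcome is written; removal is at most implied by the VARC-2 reference. The disabling count can move either way.

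**Conclusion.** The point holds in a limited form. On the written text, a non-fatal stroke that a site does not call stroke has no stated route to the CEC and cannot be added by it to the stroke or death-and-stroke results. Only the site can put it right. Any effect of this gap on the total stroke rate would be to make it too low. How often it would happen cannot be learned from the documents.

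Each missed event is worth 3.3 points in the main cohort. The 12% to 48% chance of at least one (at a 4.3% stroke rate) rests on the assumed mislabelling share and on rates from trials that excluded chronic dialysis patients. The conclusion also assumes that the CEC procedure adds no wider referral rule. The mortality primary and its power are untouched. This is an inexpensive improvement to a secondary safety result, not a threat to the trial's main conclusion.

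**What to change.** In Section 13.1 and the text introducing Table 13-1, require sites to send the CEC, up to 1 year:
- every suspected neurological event not called stroke, including TIA, transient deficit and encephalopathy;
- any rise in NIHSS from baseline at a scheduled examination, or any new lesion on head CT, when accompanied by an acute neurological deficit.

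Silent lesions alone need not be sent, because the Glossary requires acute onset of a neurological disorder.

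Have the CEC rule first stroke, TIA or neither by the Glossary, then disabling status and causality, and state that this ruling defines the endpoint. If the CEC procedure already does this, bring the protocol text into line with it.

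The cost is a small number of extra dossiers; the documents give no basis for an exact count. For the main cohort, whose enrolment is marked closed (Section 27), the review would be partly retrospective. The extra mRS assessments after an event are required only for stroke, so disabling status may have to rest on the scheduled mRS. In the registry, referral at 6 months and 1 year would depend mainly on adverse event reports. No new members are needed, since the committee already has a neurology member, and no new tests.

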14 SUBJECT TREATMENT DISCONTINUATION

14.1 Subject Treatment Discontinuation

Enrolled subjects will continuously participate in the clinical trial until all follow-up observations specified in the protocol are completed. However, the following subjects should discontinue the trial.

- A subject or the legal representative requests discontinuation of the participation in the clinical trial.
- The principal investigator or subinvestigators judges that continued trial will be a disadvantage for subject's health condition.
- The study procedure has not been started.
- When the subject is exiting the operation room, the investigational valve has not been implanted.
- The investigational valve was removed.
- The subject died.
- Continued participation in the clinical trial was deemed difficult.
- The sponsor requests (continued trial was determined to be a disadvantage in the subjects).

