	
  
 Target sample size by approach	Target sample size	A total of 30 subjects	
   
 Transfemoral	≥ 2 subjects	
 
 Transapical	≥ 2 subjects	
 
 Transaortic	≥ 2 subjects	
 
 Target sample size by valve size		
 
 20 mm	≥ 1 subject	
 
 23 mm	≥ 1 subject	
 
 26 mm	≥ 1 subject	
 
 29 mm	≥ 1 subject	
  
	Target sample size by approach	Target sample size	A total of 30 subjects	Transfemoral	≥ 2 subjects	Transapical	≥ 2 subjects	Transaortic	≥ 2 subjects	Target sample size by valve size		20 mm	≥ 1 subject	23 mm	≥ 1 subject	26 mm	≥ 1 subject	29 mm	≥ 1 subject
Target sample size by approach	Target sample size	A total of 30 subjects																		
Transfemoral	≥ 2 subjects																			
Transapical	≥ 2 subjects																			
Transaortic	≥ 2 subjects																			
Target sample size by valve size																				
20 mm	≥ 1 subject																			
23 mm	≥ 1 subject																			
26 mm	≥ 1 subject																			
29 mm	≥ 1 subject																			
Sample Size Calculation	
The sample size for this trial was calculated based on the number of subjects required to verify noninferiority of the study treatment to the standard therapy by comparing the primary endpoint of all-cause mortality at 1 year post-procedure with the performance goal (PG). With the predicted mortality (true value) at 1 year post-procedure of 20% and PG of 45%, the number of subjects required to reject the null hypothesis (H_0: Mortality at 1 year post-procedure is $\geq 45\%$) with one-sided alpha of 0.05 was calculated as 24 subjects. A sample size of 24 subjects will provide 81.1% power by one-sided Fisher's exact test. To account for the drop-out, a total of 30 subjects was determined for the target sample size for this trial.
																			

Item	Content

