As for reports in Japan, Ohno et al. reported that 26 Japanese AS patients who received drug therapy (including 2 dialysis patients) showed the mortality at 1 year post-treatment of 53.1%^[35]. That was nearly consistent with the above-mentioned PARTNER-US study results, and the mortality at 1 year post-drug therapy in Japanese non-dialysis patients was estimated as approximately 50%. Ohara et al. reported that 12 out of 16 Japanese chronic dialysis AS patients (75%) died during mean follow-up period of 32 ± 17 months,^[10] and considering that among 16 patients only 2 patients received sAVR, the mortality in 14 patients who received drug therapy may be at least 71.4% (10/14). This was similar to 3-year mortality (70.7%) in 26 AS patients (including 2 dialysis patients) reported by Ohno et al., but the mean age of patients 68 ± 10 years was significantly lower than that reported by Ohno et al. (mean age 84.1 ± 5.3 years). In addition, considering that the mean patient age in the advanced medical care given at Osaka University Hospital was 76.7 ± 5.1 years, the prognosis in the drug therapy group assumed for this clinical trial can be predicted as poorer than that reported by Ohara et al., and the 1-year mortality may be over 50%.

- 45 -

the predicted mortality at 1 year post-procedure (true value) in this clinical trial was set as 20%. As previously mentioned, the PG was set as 45%, and the number of subjects required to reject the null hypothesis (H₀: Mortality at 1 year post-procedure is ≥ 45%) with one-sided α = 0.05 was calculated as 24 subjects. A sample size of 24 subjects will provide 81.1% power by one-sided Fisher's exact test. To account for the drop-out, a total of 30 subjects was determined for the target sample size for this trial. The sample size was computed using PASS 11 software.

- PG = 45%
- Predicted mortality at 1 year post-procedure (true value) = 20%
- H₀: Mortality at 1 year post-procedure ≥ 45%
- H_A: Mortality at 1 year post-procedure < 45%
- One-sided Fisher's exact test.
- Level of significance α = 0.05

Rationale for the setting of predicted mortality at 1 year post-procedure (true value)

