7.3 Post-procedural Follow-up Observation

All subjects for whom the THV was implanted and maintained at the time point when the subject left the operation room should undergo the 5-year post-procedural follow-up observation specified in the protocol. For study discontinuation subjects without implantation of the investigational valve for the reasons that the procedure was switched to surgery, or already approved TAVI bioprosthetic valve was implanted, participation in this trial should be discontinued at the time point, and follow-up observation will not be required thereafter.

For the test/observation items and timing in the post-procedural follow-up observation, see Section 10.

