14.2 Subject Treatment Discontinuation Procedure

When a subject discontinues participation in the clinical trial, the following procedure should be used.

- The investigators should enter the date of discontinuation, reason for discontinuation, AE incidence status, and drug therapy status in the eCRFs. To ensure the safety of discontinued subjects, all possible measures should be taken, appropriate treatment should be given, and also for the safety after discontinuation, perform follow-up investigation as much as possible.
- If a subject discontinued the trial due to a safety issue arise from an incidence of AE or worsened disease, the investigators enter it in the eCRF in accordance with Section 11 "ADVERSE EVENTS."
- If an AE is found at the time of discontinuation, the investigators should perform a follow-up investigation of the AE.
- The investigators should promptly inform the sponsor of the subject's treatment discontinuation.

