30 GLOSSARY

The definitions of terms used in this clinical trial are listed below:

Term	Definition	Reference/rationale
Legally acceptable representative	A legally acceptable representative is who exercise parental authority over the subject, may also be the spouse, the guardian or the equivalent.	J-GCP
Adverse event	An adverse event (AE) is any untoward medical occurrence, unintended disease or injury, or untoward clinical signs (including abnormal laboratory findings) in subjects, users, or other persons, whether or not related to the study device. However, for an event occurred in persons other than the subjects, it should be limited to an event suspected to be associated with the use of the study device. In this clinical trial, any events developed between the start of the study procedure and the final follow-up observation (when the trial is discontinued, until the time of discontinuation) will be regarded as AEs, and events occurred between the time of informed consent and the start of the study procedure, which have not recovered at the start of the study procedure, should be handled as pre-procedural complications.	J-GCP
Serious adverse event	A serious adverse event (SAE) is an event applicable to the followings, irrespective of causal relationship to the study device. (a) Death (b) Those that may lead to death (c) Those requiring inpatient hospitalization or prolongation of existing hospitalization for treatment (d) Disability (e) Those that may lead to disability (f) Serious cases in accordance with those in (a) to (e) (g) Any congenital disease or abnormality in the offspring of a treated patient However, hospitalization without a newly developed AE or aggravated pre-procedural complication as shown in the followings is not included in SAEs. • Hospitalization for treatment scheduled before the procedure (e.g.: hospitalization for surgery for pre-procedural complication that became possible due to improvement in the heart condition) • Hospitalization for management (e.g.: regular checkup, hospitalization for examination, educational hospital admission) • Admission to a rehabilitation facility	Pharmaceutical and Medical Device Act Enforcement Regulation
Access site	The site where a guidewire, catheter, or sheath was inserted, including the artery or vein, left ventricular apex, and aorta.	
Access-related complication	An adverse clinical course that may have occurred in association with all access sites used during the study procedure.	

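### Valve removal and investigator-judged discontinuation take implanted subjects out of the trial, and nothing then secures day-365 vital status for a mortality endpoint decided by one death in 30

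*Combined protocol and SAP*

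**What the plan says.** **Who is followed.** Section 7.3: "All subjects for whom the THV was implanted and maintained at the time point when the subject left the operation room should undergo the 5-year" follow-up.

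**Who leaves.** Section 14.1 first says enrolled subjects stay until follow-up is complete, then lists exceptions. One is "The investigational valve was removed". Having no study valve on leaving the operation room is a separate item, so this one naturally covers later removal. Another is the investigator's judgement that continued participation would be to the detriment of the subject's health.

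**When event collection ends.** The glossary entry for adverse events closes the period early: "when the trial is discontinued, until the time of discontinuation". Section 11.1 runs it to the last follow-up visit and makes no such cut.

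**What happens after discontinuation.** For safety after that point, Section 14.2 asks investigators to "perform follow-up investigation as much as possible", and 10.2.9 asks for the same best effort. AEs still open are followed to recovery or stability, with exceptions (11.7; see also 14.2). The CEC reviews deaths and strokes to 1 year in all enrolled subjects, on the basis of site reports (13.1).

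**Analysis.** The primary endpoint, 1-year all-cause mortality, is tested in the AT set (15.1.1.2, 15.1.2), which is defined by the start of the procedure. Section 15 has no rule for unknown 1-year vital status, and Kaplan-Meier estimates are optional.

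**The concern.** The treatment is a one-time implant, so leaving the trial after the procedure mainly ends observation. Valve removal is itself a secondary safety endpoint (9.2.1), and subjects who reach it are unlikely to have average prognosis. If their later deaths are captured less completely than other deaths, the loss is informative and favours the device. The same applies to later stroke and re-intervention. At stake is a single-arm test on 30 subjects whose result can turn on one death.

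**Working it through.** **1. Is 1-year vital status secured after discontinuation?** Each route by which a later death could be learned of:

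- *Open AEs (11.7, 14.2).* These cover events present at discontinuation. Section 11.7 exempts, among others, cases where the investigator judges further follow-up unnecessary. New events are not covered.
- *General safety follow-up (14.2, 10.2.9).* Best effort only, with no time point and no mention of survival.
- *CEC (13.1).* The scope is all enrolled subjects to 1 year, but the committee sees only deaths that sites report.
- *Survival check (14.3).* The only explicit one. It is triggered by a missed visit, and a discontinued subject has no scheduled visit to miss.

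None of these requires vital status at day 365.

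**2. The plan's own figure.** Inputs from the synopsis and sample-size rationale: performance goal 45%; "Predicted mortality at 1 year post-procedure (true value) = 20"%; sample size "with one-sided alpha of 0.05 was calculated as 24 subjects"; "A sample size of 24 subjects will provide 81.1% power by one-sided" exact test. Taking the test as an exact binomial with success at 6 or fewer deaths in 24:

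- P(X ≤ 6 | 24, 0.45) = 0.0364
- P(X ≤ 6 | 24, 0.20) = 0.8111, which reproduces 81.1%.

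The drop-out rate is not stated; 24 / (1 − 0.20) = 30 implies 20%. Discontinued subjects are not replaced (4.3).

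**3. Decision boundary at 30.**

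- P(X ≤ 8 | 30, 0.45) = 0.0312: pass
- P(X ≤ 9 | 30, 0.45) = 0.0694: fail
- Power with complete data: P(X ≤ 8 | 30, 0.20) = 0.8713

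**4. One unseen death.** Suppose 9 subjects truly die and one death is missed. Counted alive, the data show 8/30 (p = 0.031); dropped, they show 8/29 (p = 0.043). Both pass, while the true 9/30 fails. A true count of exactly 9 has probability 0.0694 − 0.0312 = 0.038 at 45% mortality, and C(30,9) × 0.20⁹ × 0.80²¹ = 0.068 at 20%.

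**5. Effect on type I error.** Assume k of 30 subjects discontinue with vital status then unknown, each with death risk q. Hold overall true mortality at 45%, so the remaining subjects have risk (13.5 − kq)/(30 − k). The maximum passing count is 8 of 30 or 29, and 7 of 28 or 27. Neither k nor q is in the documents.

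| k | q | Dropped | Counted alive |
|---|---|---|---|
| 0 | – | 0.031 | 0.031 |
| 1 | 0.45 | 0.043 | 0.043 |
| 1 | 0.60 | 0.048 | 0.048 |
| 1 | 1.00 | 0.065 | 0.065 |
| 2 | 0.45 | 0.024 | 0.058 |
| 2 | 0.60 | 0.031 | 0.072 |
| 2 | 1.00 | 0.059 | 0.124 |
| 3 | 0.45 | 0.034 | 0.077 |
| 3 | 0.60 | 0.049 | 0.106 |
| 3 | 1.00 | 0.117 | 0.217 |

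With q = 0.45, where discontinued subjects carry no excess risk, dropping them keeps the error below 0.05. In these scenarios error above 0.05 comes from excess risk, from counting unknown subjects as alive, or from both.

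**The case against.** The strongest reply is that the plan does not abandon these subjects. A reader might infer that a subject whose valve is removed for endocarditis at month 4 and who dies at month 5 produces no serious AE report and no CEC submission. The documents do not support that. The endocarditis began before discontinuation, so it is already an AE; 11.7 and 14.2 provide for following it, and the AE record in 11.6 has fields for a fatal outcome, cause and date. Section 13.1 puts all deaths to 1 year in all enrolled subjects before the CEC, and sites must supply the documents as far as they can. Citing only the glossary cut-off would also ignore 11.1.

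Two further inferences fail. Clinical deterioration alone does not trigger discontinuation: the health ground concerns harm from continued participation. Nor does discontinuation remove anyone from the AT set. Section 14.1 lists death itself as a discontinuation, so the label cannot mean a death is uncounted.

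It can also be said that the exceptions in 14.1 were meant to qualify 7.3, that no removal rate is given, that reversal by one death needs a true count of exactly 9, and that a missing-outcome rule may sit in the separate Statistical Analysis Plan, whose text I do not have.

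All of this narrows the point. It does not close the gap in step 1: even if 14.1 is an intended exception, it stops scheduled follow-up after a device-related outcome, and an analysis rule cannot recover a death nobody recorded.

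**Conclusion.** The point stands as a should-fix. Sections 7.3 and 14.1 conflict, or at least are not cross-referenced, for implanted subjects whose valve is later removed. The glossary and 11.1 disagree on when AE collection ends. Capture of deaths after discontinuation is partial rather than absent, but day-365 vital status is not secured for a primary endpoint that needs it in every AT subject.

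The size is conditional. One unseen death reverses the result only at a true count of 9. With one to three subjects of unknown status, type I error ranges from 0.024 to 0.217 over the assumed death risks and the two ways of handling them, against 0.031 with complete data; several of these scenarios stay below 0.05. This rests on 30 AT subjects, an exact binomial test, and a one-sided reading of the 95% limit in 15.1.2. Under a two-sided 95% interval the boundary moves to 7 deaths and the argument is otherwise the same.

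**What to change.** Reconcile 7.3, 11.1, 14.1, 14.2 and the glossary so that valve removal or an investigator-judged discontinuation may stop visit tests but does not end outcome collection. The investigator's health ground can stay; deleting it would go further than the problem requires.

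Then add, for every AT subject unless consent for it is withdrawn:

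- vital status at day 365, with stroke, re-intervention and serious AE collection by record or telephone, then annual vital status to year 5;
- submission of these deaths to the CEC on the same terms as others;
- counting of these deaths in the AT primary test, with a stated rule for any subject whose status remains unknown.

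The wording should also reach AT subjects who leave the operation room without the study valve, for whom 7.3 currently asks no further follow-up.

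The cost is wording changes and probably a handful of record or telephone checks at no more than three sites. The mortality figure may be slightly less favourable. In return, complete status on 30 subjects gives 87.1% power at the assumed 20% mortality, against 81.1% if only 24 are evaluable.
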